#### **10.3** POPULATIONS FOR ANALYSIS

Modified intention to treat: all participants who receive at least one dose of each of the two agents will be included in the statistical analyses performed.

#### 10.4 STATISTICAL ANALYSES

#### 10.4.1 General approach

For participants in the primary efficacy cohort, the proportion of evaluable participants who experience a success will be reported along with a confidence interval. Safety will be evaluated by tabulating and describing the DLTs in the first 6 participants of the lead-in arm.

#### 10.4.2 Analysis of the primary endpoints

The fraction of evaluable participants who experience a success as defined above will be determined and reported along with 80% and 95% two-sided confidence intervals.

#### 10.4.3 Analysis of the secondary endpoints

Duration of response and overall survival will be estimated using a Kaplan-Meier curve based on all evaluable participants included in the two-stage cohort of the trial. The validation of the RP2D of CRLX101 in combination with enzalutamide will be done by evaluating the toxicity

and safety data obtained and the RP2D and confirming that the number of DLTs does not 1/6 in participants enrolled during the lead-in phase.

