### 3.1.1 Lead-In Component

[figure not shown]

Figure 6: Lead-In Dosing Schema and DLT Assessment

For the first 3 to 6 participants, there will be a lead-in period of two cycles to ensure the safety and tolerability of CRLX101 in combination with enzalutamide. CRLX101 will be started at a dose of 12 mg/m^2, administered via IV infusion on Day 1. Enzalutamide will be administered orally at a dose of 160 mg once daily starting on Day 2 (C1D2) once the 24-hour pharmacokinetic sample timepoint has been collected (at least 24 hours after the end of the CRLX101 infusion). After the first dose on C1D2, Enzalutamide will be taken once daily for the full duration of the study. Participants will receive CRLX101 12 mg/m^2 via IV infusion on Cycle 1 Day 15 (C1D15), Cycle 2 Day 1 (C2D1), and Cycle 2 Day 15 (C2D15). On Cycle 3 Day 1 (C3D1), and Cycle 3 Day 15 (C3D15), CRLX101 will be administered at the previously established MTD (15 mg/m^2 administered via IV infusion). Participants will be assessed from Day 1 to Day 56 (C1D1 to C2D28) for dose limiting toxicities of the CRLX101 12 mg/m^2 dose and from Day 57 to 84 (C3D1 to C3D28) for dose limiting toxicities of the CRLX101 15 mg/m^2 dose (Enzalutamide will be at approximate steady state concentration following Day 29 [C2D1]). Following the DLT assessment period (at the start of Cycle 4), each participant will continue to receive CRLX101 at the participant's specific maximum tolerated dose via IV infusion every 2 weeks (Days 1 and 15) for every subsequent cycle.

For the purposes of this study, re-assessment of the CRLX101 RP2D will be determined based on DLTs deemed likely attributable to CRLX101. DLTs are outlined in Section **3.1.1.1** and the dose modification procedures of CRLX101 are outlined in **3.3.2**. Adverse events deemed attributable to enzalutamide will not influence the on-trial treatment of subsequent participants and will be managed according to the dose modification protocol outlined in Section **3.3.3**. Final determination of the drug attributable to an adverse event is at the discretion of the Principal Investigator or designee.

If none of the three participants experience a dose limiting toxicity during the lead-in phase (Day 1-84), subsequent participants enrolled on trial with receive CRLX101 at a dose of 15 mg/m^2 via IV infusion every 2 weeks.

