If one of three participants experience intolerable toxicity during the lead-in phase, an additional 3 participants will be enrolled with no adjustments to the lead-in dosing schema. If no further toxicity is observed (or a total of 1 in 6 participants experience dose-limiting toxicity),

subsequent participants enrolled on study will receive CRLX101 at a dose of 15 mg/m^2 every 2 weeks. If 2 of 6 participants experience a dose limiting toxicity, the dose at which the DLT occurred will determine further action:

- If both participants experience a DLT attributable to CRLX101 at a dose of 15 mg/m^2 or only one participant experiences a DLT at 12 mg/m^2, subsequent participants will receive CRLX101 at 12 mg/m^2 every 2 weeks.
- If both participants experience a DLT attributable to CRLX101 at a dose of 12 mg/m^2, participants will be given one dose of CRLX101 at 9 mg/m^2.
  - If further toxicity is observed with the 9 mg/m^2 dose, an amendment to modify dosing strategies will be considered. If necessary, the RP2D will be determined at the discretion of the Principal Investigator or designee after factoring in participant specific characteristics and the nature of the adverse event.

[figure not shown]
Based on limited potential for overlapping toxicity and well-characterized pharmacokinetics for both enzalutamide and CRLX101, it is anticipated 3 participants will participate in the lead-in phase. An accrual ceiling of 6 participants for the lead-in phase will be used to account for possible dose adjustments based on DLTs.

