Following the DLT assessment during the lead-in component and validation of the RP2D, participants enrolled thereafter will not participate in the lead-in period. Participants will receive CRLX101 at the RP2D established during the lead-in component via IV infusion on Cycle 1 Day 1 (C1D1). Enzalutamide will be administered orally at a dose of 160 mg once daily beginning on Cycle 1 Day 2 (C1D2), at least 24 hours after the end of the infusion of CRLX101. After the first dose on C1D2, Enzalutamide will be taken once daily for the full duration of the study. Participants will receive CRLX101 at the established RP2D via IV infusion on C1D15 and on Days 1 and 15 of each subsequent cycle.

Following establishment of the RP2D, enrollment on this study will continue until 8 participants are evaluable for the primary endpoint. If 3 or more participants achieve response, then additional participants will be enrolled until a total of 21 participants have been evaluated for the primary endpoint. The accrual ceiling is set for 30 participants, to account for participants that are inevaluable or participants that do not tolerate treatment in the lead-in phase. For more details, refer to Section 8.

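### The numeric check that is meant to validate the RP2D names no dose and only repeats the dose-selection step, and the two-stage participants treated at the RP2D get no DLT count

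*Combined protocol and SAP*

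**What the plan says.** Secondary objective 1.1.2.2 is to validate the RP2D of CRLX101 with enzalutamide. Section 10.4.3 does this in two limbs. The first evaluates toxicity "and safety data obtained and the RP2D", where 'and' probably stands for 'at'; it has no threshold. The second is "confirming that the number of DLTs does not 1/6 in participants enrolled during the lead-in phase".

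Section 3.1.1 gives each lead-in participant two dose periods in sequence. "Participants will be assessed from Day 1 to Day 56 (C1D1 to C2D28) for dose limiting toxicities of the CRLX101 12 mg/m 2 dose", and then "from Day 57 to 84 (C3D1 to C3D28) for dose limiting toxicities of the CRLX101 15 mg/m 2 dose". The dose-selection rule runs across both periods. It begins "If none of the three participants experience a dose limiting toxicity during the lead-in phase (Day 1-84", in which case 15 mg/m² is kept; it is also kept when the total is 1 of 6. After 2 of 6, the dose at which the DLTs occurred decides. If neither or only one was at 12 mg/m², "subsequent participants will receive CRLX101 at 12 mg/m 2 every 2 weeks". If both were at 12 mg/m², the text moves to 9 mg/m².

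Later participants skip the lead-in: "Participants will receive CRLX101 at the RP2D established during the lead-in component via IV infusion on Cycle 1 Day 1 (C1D1"). For DLTs, Section 10.4.1 says: "Safety will be evaluated by tabulating and describing the DLTs in the first 6 participants of the lead-in arm". Section 10.4.4 reports grade 3 and grade 4 adverse event fractions for everyone treated, with the efficacy cohort separate from the lead-in. It defines no DLT count for that cohort.

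**The concern.** A validation step should be able to tell a dose that holds up from one that does not. The limit of 1/6 in 10.4.3 is the same number that 3.1.1 uses to keep 15 mg/m², counted in the same 3 to 6 people. The result may therefore be settled once the dose has been chosen. If the count is pooled over doses, the plan can also select a dose under 3.1.1 and then be unable to confirm it under 10.4.3.

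The people who could supply new information are the 8 to 21 in the two-stage part. They have no DLT tabulation. What is at stake is the conclusion on a secondary objective, and the tolerability evidence carried into any later trial.

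**Working it through.** **Plan's own figure.** The documents give no operating characteristics for the 1/6 check, so there is none to reproduce.

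**Step 1: every outcome for which 3.1.1 names a dose, set against 1/6** (missing verb read as 'exceed').

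| Lead-in participants with a DLT | Dose under 3.1.1 | DLTs pooled over doses | DLTs at the chosen dose only |
|---|---|---|---|
| 0/3 | 15 mg/m² | 0/3, meets | 0/3, meets |
| 1/6 | 15 mg/m² | 1/6, meets | 0/6 or 1/6, meets |
| 2/6, none or one at 12 mg/m² | 12 mg/m² | 2/6, fails | 0/6 or 1/6, meets |
| 2/6, both at 12 mg/m² | 9 mg/m² | 2/6, fails | no lead-in cohort at 9 mg/m² |

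Within each column, the chosen dose fixes the result, whatever the true DLT rates are.

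**Step 2: how often the dose is lowered.** The documents give no DLT rates, so these are assumptions. Let a be the risk at 12 mg/m² and b the risk at 15 mg/m² in a participant without a DLT at 12 mg/m². Participants are independent and each counts once. The risk over Days 1-84 is d = 1 − (1−a)(1−b). A lowered dose needs one DLT in each group of three: P = [3d(1−d)²]².

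- a = b = 5%: d = 0.0975, P = 0.057.
- a = b = 10%: d = 0.19, P = 0.140 (0.101 for 12 mg/m², 0.039 for 9 mg/m²).
- a = 15%, b = 20%: d = 0.32, P = 0.197.

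With a total risk of 20% the same formula gives (0.6 × 0.64)² = 0.147; with 30%, (0.9 × 0.49)² = 0.194. The sharpest case has both DLTs at 15 mg/m² and none at 12 mg/m². At a = b = 10% its probability is [3 × 0.09 × 0.81²]² = 0.031.

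**Step 3: how much a pass says.** The rule of 0/3 or 1/6 passes with probability (1−p)³ + 3p(1−p)⁵ at a total DLT rate p.

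- p = 30%: 0.343 + 0.151 = 0.494.
- p = 40%: 0.216 + 0.093 = 0.309.

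**Step 4: precision.** Exact (Clopper-Pearson) 95% limits are the 0.025 quantile of Beta(x, n−x+1) and the 0.975 quantile of Beta(x+1, n−x).

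- 0/3: 0 to 70.8%.
- 1/6: 0.4% to 64.1%.
- 2/21, illustrative only: 1.2% to 30.4%.

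**Step 5: exposure.** Lead-in infusions 1 to 4 (C1D1, C1D15, C2D1, C2D15) are at 12 mg/m²; infusions 5 and 6 (C3D1, C3D15) are at 15 mg/m². If the RP2D is 15 mg/m², the lead-in therefore observes it over two infusions and 28 days, after four lower doses. Two-stage participants receive the RP2D from infusion 1.

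**The case against.** The strongest reply is that the sentence in 10.4.3 is corrupted and nowhere says that doses are pooled. Section 3.1.1 assigns DLTs to a dose by time window and acts on the dose at which they occurred, so a dose-specific count is a fair reading. On that reading an RP2D of 12 mg/m² always passes and nothing conflicts. This stands: a reader might infer that a lowered RP2D fails whatever the sentence means, and the documents do not support that. It does not rescue the check, because a test that 15 and 12 mg/m² cannot fail, and that cannot be run for 9 mg/m², is also uninformative.

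A reader might also infer that toxicity in the two-stage cohort plays no part in validation. That is too strong. The first limb of 10.4.3 and Section 10.4.4 bring those participants in descriptively; only the numeric limb and the DLT tabulation leave them out. Nor is it right that the lead-in never starts at the RP2D: if the RP2D is 12 mg/m², it does. The possible conflict arises only for a lowered dose, and the late-exposure point applies to 15 mg/m², so the two should not be added together.

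Lastly, confining DLTs to a lead-in is ordinary practice, and the pass rates in step 3 describe any lead-in of this size. Section 3.3.2.2.1 bars prophylactic growth factors in lead-in cycles 1 to 3 but permits them in the Phase 2 stage, so neutropenic DLTs are not directly comparable. These points stand. They limit what a two-stage DLT fraction can show, but do not make it worthless.

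**Conclusion.** The concern holds in a limited form. The only numeric criterion for validating the RP2D lacks a verb and a dose, and on either reading it repeats what dose selection has already settled. Pooling is the more natural reading, because 1/6 matches the total of 1 in 6 in Section 3.1.1. On that reading Sections 3.1.1 and 10.4.3 disagree whenever the dose is lowered: about 6-20% of trials over the assumed risks of 5%/5% to 15%/20%, or 15-19% at assumed total rates of 20-30%.

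A pass is weak evidence, with probability 0.49 at an assumed true DLT rate of 30% and 0.31 at 40%. The larger cohort, which receives the RP2D as it would be used, has no DLT summary.

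The consequence is confined to secondary objective 1.1.2.2. Dosing is governed by Section 3.1.1, and the primary analysis does not depend on 10.4.3.

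**What to change.** (a) In 10.4.3, restore the missing verb, state which dose's DLTs are counted, and reconcile the sentence with the dose-selection rule in 3.1.1. Which dose or rule is right is not for this review to say. This step removes the ambiguity but does not by itself make the check informative.

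(b) Also in 10.4.3, apply the DLT definitions of Section 3.1.1.1, with their 84-day window, to two-stage participants treated at the RP2D. Report the fraction with a DLT and its exact 95% CI, separately from the lead-in. Include it as a descriptive summary at the stage-1 look in 10.4.6. The primary assessment is at C6D1, day 5 × 28 + 1 = 141, so the window will have closed by then.

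The cost is wording and some derivation, with no added participants or visits. Adverse event data alone are not enough, because the definitions also use missed cycle 1 doses, delays of more than two weeks and the duration of cytopenias. Laboratory and dosing records are needed as well. Growth-factor use should be shown beside the result because the cohorts follow different rules.

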## 10.4.4 Safety Analyses

Safety of the agent will be assessed by determining the grade of adverse events noted in each participant, and reporting the fraction with grade 3 and grade 4 adverse events. Participants who receive at least one dose of the study treatments will be evaluable for safety. Safety data will be presented in a summary. Results from the safety evaluation in the initial 3-6 participant safety cohort will be reported separately from safety data from participants included in the efficacy cohort. The safety data will consist of the reporting of all adverse events, and may also include reporting vital signs, physical examination data, and laboratory safety data.

## 10.4.5 Baseline Descriptive Statistics

Limited demographic and clinical characteristics of all participants will be reported.

10.4.6 Planned interim analyses

An evaluation of the safety data based on the initial 3-6 participant lead-in cohort will be performed prior to enrollment of participants in the efficacy cohort. As indicated in the sample size determination section, an interim evaluation of the number of participants who experienced a success in the first stage of the two-stage optimal design will be performed to ensure that enrollment to the second stage is warranted.

## 10.4.7 Exploratory analyses

The following are the intended exploratory objectives:

- To evaluate the pharmacokinetic profile of CRLX101 (both total drug and released camptothecin) and enzalutamide in plasma;
- To evaluate underlying mechanisms of camptothecin-induced cystitis;
- To evaluate the pharmacodynamic activity of CRLX101 and enzalutamide using surrogate biomarkers to measure acquired treatment resistance mediated by angiogenesis and androgen receptor signaling (e.g. VEGF, CTCs, AR-V7);
- To evaluate the activity of CRLX101 and enzalutamide with respect to the prevalence of circulating tumor cells with high genomic instability;
- To explore possible correlations between clinical response and biomarkers of DNA damage response (e.g. PAR up-regulation, DNA damage response panel).

Any exploratory evaluations which generate quantitative measures will be done using descriptive statistics including confidence intervals when appropriate. Any statistical tests performed for evaluation of exploratory objectives will be done without formal adjustment for multiple comparisons, but in the context of the number of tests performed.

## **11 COLLABORATIVE AGREEMENTS**

## 11.1 COOPERATIVE RESEARCH AND DEVELOPMENT AGREEMENT (CRADA)

## 11.1.1 Ellipses Pharma

The investigational study agent, CRLX101 is provided by the company, Ellipses Pharma under MTA # 45025-18 executed 10/10/2018, under CRADA # 03089.

## **12 HUMAN SUBJECTS PROTECTIONS**

## 12.1 RATIONALE FOR SUBJECT SELECTION

Subjects treated on this study will be individuals with metastatic castration resistant prostate cancer, which has recurred (or persisted) after appropriate treatment. Men of any race or ethnic group will be eligible for this study. Eligibility assessment will be based solely on the participant's medical status. Women will not be eligible as the disease under study is not present in this population. Recruitment of participants onto this study will be through standard CCR mechanisms. No special recruitment efforts will be conducted.

## 12.2 PARTICIPATION OF CHILDREN

Individuals under the age of 18 will not be eligible to participate in this study because they are unlikely to have prostate cancer, and because of unknown toxicities of CRLX101 in combination with enzalutamide in the pediatric participant.

## 12.3 PARTICIPATION OF SUBJECTS UNABLE TO GIVE CONSENT

Adults unable to give consent are excluded from enrolling in the protocol. However, re-consent may be necessary and there is a possibility, though unlikely, that subjects could become decisionally impaired. For this reason and because there is a prospect of direct benefit from research participation (section 12.4), all subjects  $\geq$  age 18 will be offered the opportunity to fill in their wishes for research and care, and assign a substitute decision maker on the "NIH Advance Directive for Health Care and Medical Research Participation" form so that another person can make decisions about their medical care in the event that they become incapacitated or cognitively impaired during the course of the study.

Note: The PI or AI will contact the NIH Ability to Consent Assessment Team (ACAT) for evaluation to assess ongoing capacity of the subjects and to identify an LAR, as needed.

# 12.4 Please see section 12.6.1 For consent procedure. Evaluation of Benefits and Risks/Discomforts

The potential benefit to a participant that goes onto study is a reduction in the bulk of their tumor and improvement in their bony lesions, which may or may not have favorable impact on symptoms and/or survival. Potential risks include the possible occurrence of any of a range of side effects which are listed in the Consent Document. The procedure for protecting against or minimizing risks will be to medically evaluate participants on a regular basis.

## 12.5 RISKS/BENEFITS ANALYSIS

For participants with castration resistant prostate cancer, median survival is in the range of 12-18 months. Enzalutamide has shown activity against prostate cancer in a clinical setting. CRLX101 has demonstrated clinical activity to down-regulate HIF-1 $\alpha$  in ovarian cancer and *in vitro* 

assessments examining the down-regulation of HIF-1 $\alpha$  in combination with enzalutamide have demonstrated a synergistic effect, decreasing angiogenesis and androgen receptor signaling in LNCaP cell models. Preclinical assessments (*in vitro* and *in vivo*) examining this treatment combination are currently ongoing. Although possible toxicities from the proposed therapy are serious, given the nature of the underlying disease, they are reasonable. Additionally, we do not anticipate toxicities significantly more severe than those observed with other approved agents. For these reasons, the risk/benefit ratio of this protocol is favorable; therefore, this protocol involves greater than minimal risk to all participants on study, but presents the potential for direct benefit to all individual subjects enrolled on study.

**NOTE:** This same risks/benefits analysis applies to all study populations included in this clinical study.

#### 12.5.1 Risks related to Imaging

CT scans and TC-99 scas often use a contrast agent. There is a small risk of having a reaction to the contrast and most often include nausea, pain in the vein where the contrast is given, headache, metallic and/or bitter taste in the mouth and a warm, flushing feeling. Rarely, some people have more severe allergic reactions to the contrast which may include skin rashes, shortness of breath, wheezing or low blood pressure.

#### 12.5.2 Risks from Radiation Exposure

The procedures for performing the CT scans (chest/abdomen/pelvis) and Tc-99 whole body scintography scans will follow clinical policies, no special procedures apply to these additional assessments for research purposes. In summary, subjects may receive additional radiation exposure in one year from up to four (4) CT scans of the chest, abdomen, and pelvis, and four (4) Tc-99 whole body scintography scans. Radiation exposure is associated with an increased risk of cancer.

#### 12.6 CONSENT PROCESS AND DOCUMENTATION

The informed consent document will be provided to the participant or consent designee(s) as applicable for review prior to consenting. A designated study investigator will carefully explain the procedures and tests involved in this study, and the associated risks, discomforts and benefits. In order to minimize potential coercion, as much time as is needed to review the document will be given, including an opportunity to discuss it with friends, family members and/or other advisors, and to ask questions of any designated study investigator. If a prolonged period of time expires during the decision making process (several weeks, as an example), it may be necessary to reassess the participant for protocol eligibility. A signed informed consent document will be obtained prior to entry onto the study.

Re-consent, when required, may take place in person or remotely (e.g., via telephone or other NIH approved remote platforms) per discretion of the designated study investigator and with the agreement of the participant. Whether in person or remote, the privacy of the subject will be maintained. Consenting investigators (and participant, when in person) will be located in a private area (e.g., clinic consult room). When re-consent is conducted remotely, the participant will be informed of the private nature of the discussion and will be encouraged to relocate to a more private setting if needed.

12.6.1 Consent Process for Adults Who Lack Capacity to Consent to Research Participation

For participants addressed in section **12.3**, an LAR will be identified consistent with Policy 403 and informed consent obtained from the LAR, as described in Section **12.6**.

## **13 REGULATORY AND OPERATIONAL CONSIDERATIONS**

## 13.1 STUDY DISCONTINUATION AND CLOSURE

This study may be temporarily suspended or prematurely terminated if there is sufficient reasonable cause. Written notification, documenting the reason for study suspension or termination, will be provided by the suspending or terminating party to study participants, investigator, funding agency, the Investigational New Drug (IND) sponsor and regulatory authorities. If the study is prematurely terminated or suspended, the Principal Investigator (PI) will promptly inform study participants, the Institutional Review Board (IRB), and sponsor and will provide the reason(s) for the termination or suspension. Study participants will be contacted, as applicable, and be informed of changes to study visit schedule.

Circumstances that may warrant termination or suspension include, but are not limited to:

- Determination of unexpected, significant, or unacceptable risk to participants
- Demonstration of efficacy that would warrant stopping
- Insufficient compliance to protocol requirements
- Data that are not sufficiently complete and/or evaluable
- Determination that the primary endpoint has been met
- Determination of futility

Study may resume once concerns about safety, protocol compliance, and data quality are addressed, and satisfy the sponsor, IRB and as applicable, Food and Drug Administration (FDA).

